10.3 Analysis Population

The following populations are defined:

Population	Description
Enrolled	All participants who sign the ICF
Evaluable	All participants in whom a neuraxial procedure is attempted, regardless of success

10.4 Primary Endpoints

The incidence rate for the primary safety endpoints will be calculated as the number of participants experiencing the event divided by the total number of evaluable patients; 95% confidence interval (exact method) will be calculated. The same approach will be used for primary efficacy endpoints.

10.5 Secondary Endpoint(s)

For each complication listed as a secondary endpoint, the incidence of each complication will be calculated by dividing the number of participants experiencing the event by the total number of participants; 95% confidence intervals will be calculated where appropriate.

10.6 Other Analyses

Protocol Number: MDS-20EPSPEU001

CONFIDENTIAL

Version: 3.0

Date: 27Apr2022

For other data not specifically captured under primary or secondary endpoints (e.g., participant position; medications administered), summary statistics for categorical variables will include frequency counts and proportions and for continuous variables mean, standard deviation, minimum, median and maximum. Further details will be included in the final Statistical Analysis Plan (SAP).

11 DATA COLLECTION AND RECORD MAINTENANCE

11.1 Case Report Forms

The Investigator is responsible for ensuring the completeness and accuracy of all study documentation.

All required clinical data will be collected/document in sponsor-provided electronic Case Report Forms (CRFs). Applicable national and local regulations are followed on the handling of electronic data. Modification of the CRFs will only be made if deemed necessary by the Sponsor and/or the appropriate regulatory body.

Site numbers and participant numbers will be used to track participant information throughout the study. Participant personal information will be pseudonymized/de-identified.

11.2 Source Documentation

Original or certified copies of all relevant clinical findings, observations, and other activities throughout the clinical investigation must be recorded and maintained in the medical and/or study file of each enrolled participant. Where there is no prior written or electronic record of data, such as clinical surveys, these data may be recorded directly on the CRF(s) and the CRF is then considered to be the source.

11.3 Data Management

Data management is the responsibility of the Sponsor or their designee. Data from completed CRFs will be managed in a secured, controlled database. A Data Management Plan (DMP) will be developed that outlines the procedures used for recording, data tracking, data review, database cleaning, issuing/resolving data queries and securing of electronic data system as well as the procedures for validations and data storage will also be contained within the DMP.

11.4 Record Retention

The Investigator shall retain all study records for a minimum of ten (10) years after the date on which the study is terminated/completed. Study records may be stored longer if required by national law or other local rules. The data for some of these records may be

Protocol Number: MDS-20EPSPEU001

CONFIDENTIAL

Version: 3.0

Date: 27Apr2022

available in computerized form but the final responsibility for maintaining study records remains with the Investigator.

The Investigator may withdraw from the responsibility to maintain records for the period required by transferring custody of the records to any other person who will accept responsibility for retaining them. Notice of a transfer shall be given to the Sponsor not later than ten (10) working days after the transfer occurs.

12 QUALITY CONTROL AND ASSURANCE

12.1 Control of Study Products

In this observational, real-world study, shelf-stock of study devices will be used. Clinicians may choose and use any study device that is available for use in their institution and that is medically appropriate for use in study participant. No special controls are required in this study.

12.2 Monitoring

The Sponsor will designate trained and qualified personnel to monitor the progress of this clinical study in accordance with established standard operating procedures and the study-specific Monitoring Plan.

Prior to study start, a study initiation visit (SIV) will be conducted to review with the Investigator(s) and staff the provisions and proper conduct of this study. This visit will include a detailed review of this protocol, verification that all necessary documents are on file at the investigational site and confirmation of IRB/EC approvals.

During the study, routine monitoring visits (RMVs) will be conducted to assure the site continues to adhere to the protocol, the investigator agreement, and regulations regarding conduct of clinical studies. The Monitor will confirm that the ICF to be used is the version approved by the IRB/EC, confirm the applicable national privacy laws have been followed, verify that all necessary documents are on file at the investigational site and confirm that there are provisions to continue and maintain all documents and records throughout the study as required by applicable regulations. These monitoring visits will assess continued protocol compliance, adequate participant enrollment, accurate data reporting, monitoring of participant safety through identification and/or review of any device-related AEs, UADEs, or SAEs, device accountability, continued maintenance and calibration of study-specific equipment (if applicable), and continued IRB/EC acceptance of the study.

At the completion of the study, the Monitor will conduct a final close-out visit (COV). The purpose of this visit may include but is not limited to collecting all outstanding study data documents, confirming that the Investigator's files are accurate and complete, reviewing the record retention requirements with the Investigator, ensuring that all applicable requirements for closure of the study are met.

12.3 Audits and Inspections

If the study is selected for audit by the Sponsor or if there is an inspection by the appropriate Health Authorities, the Investigator and her/his team will make themselves available during the visit. The Investigator must agree to the inspection of all study related records and give the auditor/inspector direct access to source documents for verification of data on CRFs. The participant's anonymity must be ensured, and data checked during the audit must remain confidential.

As soon as the Investigator is aware of an upcoming inspection/audit by the Health Authorities, he/she will promptly inform the Sponsor. As agreed with the Investigator, Sponsor personnel may be present at the site during the inspection.

12.4 Protocol Deviations

A protocol deviation is defined as an event where the Investigator or site personnel did not conduct the study according to the protocol.

Except when necessary to protect the life or physical well-being of a participant, protocol deviations are not permitted. The Sponsor and the investigational site's IRB/EC must be notified immediately if an emergency situation arises in which the safety of a participant may require immediate intervention different than that defined in the protocol. This must be followed by written confirmation that describes the emergency action and outcomes, within five (5) working days from the date of the emergency action in accordance with the governing IRB/EC's requirement.

It is the Investigator's responsibility to ensure that there are no deviations from the Protocol. Except in an emergency, when a protocol deviation is planned or anticipated, the Sponsor should be contacted for approval. Any and all deviations must be recorded on the appropriate CRF regardless of whether medically justifiable or sponsor approved. Upon evaluation by the Sponsor, actions may be required to prevent additional deviations, such as retraining of the site, implementation of additional site procedures, and more frequent monitoring. If these steps fail, more serious measures, up to and including termination of enrollment at the site.

13 ADMINISTRATIVE REQUIREMENTS

13.1 Investigator and Site Selection

The Investigator must be of good standing as an Investigator and knowledgeable in relevant areas of clinical research to ensure adherence to the requirements of this protocol, including the protection of human participants. Other site personnel must have appropriate research experience and infrastructure to ensure adherence to this protocol

Protocol Number: MDS-20EPSPEU001

CONFIDENTIAL

Version: 3.0

Date: 27Apr2022

and enrollment of sufficient numbers of evaluable participants. The curriculum vitae (CV) of the Investigator(s), Sub-Investigator(s) and Study Coordinator(s) will be maintained in the Sponsor's files as documentation of qualification by training and experience.

The Principal Investigator will sign the Investigator Agreement pages of this protocol, agreeing to comply with all applicable regulations and the requirements of this study per the clinical study agreement.

Any site that is deactivated prior to initial enrollment, either by the Sponsor or by the individual site itself, may be replaced.

13.2 Training

Each Investigator and appropriate site personnel will be trained on this protocol, study requirements and if needed study devices during the Site Initiation Visit. All training will be documented and filed at the investigational site and with the Sponsor.

13.3 Required Documents

An Investigator may not screen or enroll participants until authorized to do so by the Sponsor. At a minimum, the following documentation should be received by the Sponsor prior to the commencement of study activities:

- Fully executed Non-disclosure Agreement (NDA) between PI/site and Sponsor;
- CVs, signed and dated within 2 years of study start for the PI and Sub-Investigator(s);
- CVs for Study Coordinator(s);
- Signed CSA by PI/site (or designee);
- Signed Protocol Signature Page by PI;
- Signed Financial Disclosure Statement by PI and Sub-Investigator(s)]
- Completed and Signed Training Log by PI and Sub-Investigator(s);
- Study Personnel Identification list]
- Written approval from the IRB/EC of both the protocol and ICF, and any other applicable protocol specific material; and
- IRB/EC Membership List, Assurance of Compliance Form, or equivalent.

13.4 Insurance

Where required by local regulation, insurance coverage will be provided by BD for study participants.

13.5 Publication Policy

Protocol Number: MDS-20EPSPEU001

CONFIDENTIAL

Version: 3.0

Date: 27Apr2022

The sponsor believes that results of applicable clinical studies should be published in peer-reviewed literature in a timely, accurate, complete and balanced manner, regardless of study outcomes, whenever possible. As such, at the conclusion of this study, an article may be prepared for publication in a reputable scientific journal. Formal presentation(s) or publication(s) of data collected from this study will be considered as a joint publication by the investigator(s) and the appropriate personnel of the Sponsor. Authorship will be based on generally accepted criteria of the ICMJE (International Committee of Medical Journal Editors) and determined by mutual agreement.

The publication of the principal results from any single-center experience within the study is not allowed until the preparation and publication of the multicenter results. Exceptions to this rule require the prior approval of the Sponsor. The analysis of other pre-specified and non-pre-specified endpoints will be performed by the Sponsor or its designee. Such analyses, as well as other proposed investigations or manuscripts will require the approval of the Sponsor.

13.6 Study Registration

While this is a non-interventional study and does not meet the FDA Amendments Act of 2007 (FDAAA) criteria for clinical study registration, the study will be registered on www.clinicaltrials.gov. The Sponsor will register the study on local registries if applicable. The content of the publicly accessible database(s) will be updated throughout the conduct of the clinical study and the results will be entered after study completion in order to make publicly available the results of the study.

13.7 Termination of Study

The Sponsor reserves the right to suspend enrollment or terminate the study at any time for any reason. If suspicion of an unacceptable risk, including serious health threat to subjects, arises during the study, the Sponsor may suspend the study while the risk is assessed. The sponsor shall terminate the clinical investigation if an unacceptable risk which cannot be controlled is confirmed.

The Sponsor may suspend enrollment or terminate the study at a specific investigational site for reasons including, but not limited to, inadequate data collection, low participant enrollment rate, achievement of the total enrollment, conditions imposed by the reviewing IRB/EC and/or non-compliance with this protocol or other clinical research requirements. Written notice will be submitted to the Investigator in advance of such termination.

In the event of study suspension or termination, the Sponsor will send a report outlining the circumstances to the IRB/EC, and all Investigators and Regulatory Authorities as required by regulation.

14 ETHICAL AND REGULATORY CONSIDERATIONS

14.1 IRB/EC Approval

Investigators or designees must submit the study protocol, Informed Consent Form (if applicable), and all other locally required documentation to an appropriate IRB/EC and obtain study-specific written approval (favorable opinion) before being allowed to participate in the study. Before commencement of the study, the Investigator or designee must provide the Sponsor with written documentation of such approval. The IRB/EC must give written renewal of the original approval at least annually to continue the study, if applicable per local regulations. A copy of the written renewal must be provided to the Sponsor.

The IRB/EC will be notified of any amendments to the protocol, as well as possible associated information and consent form changes, where applicable, and written approval (favorable opinion) will be obtained prior to implementation, as applicable.

The Investigator or designee is responsible for fulfilling any conditions of approval imposed by the IRB/EC, such as regular safety reporting, study timing, etc. The Investigator or designee will provide the Sponsor with copies of such reports.

14.2 Informed Consent and Confidentiality

Prior to any study activity, the Investigator (or designee) must explain to each participant* in layman's terms, the nature of the study, its purpose, expected duration, and the risks and benefits of study participation. Also, the participant* will be informed of uses and disclosures of their medical information for research purposes, and their rights to access information about them. All applicable national privacy laws (e.g., General Data Protection Regulation [GDPR] requirements in the E.U.) will be followed in this study. The participants* must be informed of their right to withdraw from the study at any time and for any reason without sanction, penalty, or loss of benefits to which they are otherwise entitled, and that withdrawal from the study will not jeopardize their future medical care. Participants* will be informed of their right to new information and/or findings relating to the clinical study, and the process by which this information is made available. After this explanation, given sufficient time to decide whether to participate before entering the study, the participant* must voluntarily provide consent by signing the form, including date and time of signature, in accordance with ISO 14155. The participant* will receive a copy of his/her signed ICF. The informed consent process should be documented in the participant's medical record.

*Note: If the participant is under the age of 18 years, participants' parent(s) or legal guardian must provide their informed consent and the child must provide assent, depending on local EC requirements, by personally signing and dating the respective consent form prior to begin of this study.

Protocol Number: MDS-20EPSPEU001

CONFIDENTIAL

Version: 3.0

Date: 27Apr2022

14.3 Confidentiality

Participant confidentiality must be strictly held in trust by the Investigator, study staff, and the Sponsor. Participant confidentiality and anonymity will be maintained by removal of identifiers from any data, documentation, or clinical samples submitted to the Sponsor.

Any data collected meeting the definition of protected/confidential health information or personal identifying information will be collected and maintained using the designated authorizations and following privacy procedures as specified in the applicable regulatory authority regulations including the European Union General Data Protection Regulation (GDPR).

The Sponsor Monitor, authorized representatives of the sponsor, and/or applicable regulatory authorities may inspect all documents and records required to be maintained by the Investigator. The Investigator/Site will permit access to such records.

14.4 Regulatory Status

The study devices are CE marked and will be studied in a post-market fashion in Europe.

14.5 Statement of Compliance

This clinical investigation will be conducted in compliance with the protocol and following regulatory requirements:

- ISO14155:2020 (Good Clinical Practice);
- EU MDR (Council Regulation 2017/745 of 5 April 2017);
- Ethical principles of the Declaration of Helsinki, in its current revision; and
- Applicable sections of the national laws and regulations.

The clinical investigation will not commence at a clinical site until approval (favorable opinion) from the respective IRB/EC has been received. All additional requirements imposed by the IRB/EC(s) will be followed. Involvement of the national competent authorities (e.g., by notification, seeking authorization) will be accomplished as required by national laws and regulations.

16 APPENDICES

16.1 BD Spinal Needles

Needle Type	Catalog Number	Description
Whitacre	401995	22 G x 90 mm (3 1/2 in.)
Whitacre	405104	24 G x 90 mm (3 1/2 in.), Thin Wall
Whitacre	402050	25 G x 90 mm (3 1/2 in.), Thin Wall
Whitacre	402051	27 G x 90 mm (3 1/2 in.)
Quincke	405247	18 G x 75 mm (3 in.)
Quincke	405248	18 G x 90 mm (3 1/2 in.)
Quincke	405249	19 G x 75 mm (3 in.)
Quincke	405250	19 G x 90 mm (3 1/2 in.)
Quincke	405251	20 G x 38 mm (1 1/2 in.)
Quincke	405252	20 G x 75 mm (3 in.)
Quincke	405253	20 G x 90 mm (3 1/2 in.)
Quincke	405254	22 G x 38 mm (1 1/2 in.)
Quincke	405244	22 G x 64 mm (2 1/2 in.)
Quincke	405255	22 G x 75 mm (3 in.)
Quincke	405256	22 G x 90 mm (3 1/2 in.)
Quincke	405240	23 G x 90 mm (3 1/2 in.)
Quincke	405245	25 G x 51 mm (2 in.)
Quincke	405257	25 G x 90 mm (3 1/2 in.)
Quincke	405246	25G x 75 mm (3.5 in.)
Quincke	405234	25 G x 119 mm (4 11/16 in.)
Quincke	405258	26 G x 90 mm (3 1/2 in.)
Quincke	405259	27 G x 90 mm (3 1/2 in.)
Quincke	405243	25 G x 25 mm (1 in.), Neonatal Lumbar
Quincke	408360	18G x 156 mm (6 in.)
Quincke	405211	20 G x 156 mm (6 in.)
Quincke	405148	22 G x 127 mm (5 in.)
Quincke	405149	22 G x 178 mm (7 in.)
Whitacre	409442	25 G x 119 mm (4 11/16 in.)
Whitacre	409443	27 G x 119 mm (4 11/16 in.)

Protocol Number: MDS-20EPSPEU001

CONFIDENTIAL

Version: 3.0

Date: 27Apr2022

Kit/Set Needle Type	Catalog Number	Description
Whitacre	405076	25 G x 90 mm BD™ Whitacre spinal needle, Thin Wall
Whitacre	405075	27 G x 90 mm BD™ Whitacre spinal needle
Whitacre	405112	25 G x 103 mm (4-1/16 in.) Whitacre Set
Whitacre	405113	27 G x 103 mm (4 1/16 in.) Whitacre Set
Quincke	405084	25 G x 90 mm BD™ Quincke spinal needle
Quincke	405065	26 G x 90 mm BD™ Quincke spinal needle
Quincke	405069	27 G x 90 mm BD™ Quincke spinal needle
Quincke	405068	29 G x 90 mm (3 1/2 in.) Spinal Set

Signature Page for VV-TMF-247774 v1.0

Reason for signing: Finalize	Name: [name] Role: Clinical Project Management Date of signature: 27-Apr-2022 12:09:58 GMT+0000
Reason for signing: Finalize	Name: [name] Role: Medical Monitor Date of signature: 27-Apr-2022 18:28:40 GMT+0000
Reason for signing: Finalize	Name: [name] Role: Regulatory Affairs Date of signature: 29-Apr-2022 16:15:12 GMT+0000
Reason for signing: Finalize	Name: [name] Role: Statistics & Programming Date of signature: 29-Apr-2022 17:12:31 GMT+0000

Signature Page for VV-TMF-247774 v1.0

## List of Abbreviations and Definitions

ADE	Adverse Device Effect
AE	Adverse Event
BD	Becton Dickinson and Company
CRF	Case Report/Record Form
CSF	Cerebrospinal Fluid
ICF	Informed Consent Form
PDPH	Post-Dural Puncture Headache
PT	Preferred Terms
SADE	Serious Adverse Device Effect
SAE	Serious Adverse Event
SAP	Statistical Analysis Plan
SD	Standard Deviation
SOC	System Organ Class

## 1 Introduction

### 1.1 Background and Rationale

This study is designed to assess the safety and performance of the BD Spinal Needles mainly, but not limited to the purpose of providing clinical data required under EU regulation 2017/745.

### 1.2 Objectives and Endpoints

Objectives	Endpoints
Primary Safety	
Spinal Needle: Assess the incidence of post-dural puncture headache (PDPH)	Percentage of participants with a diagnosis of PDPH in the 7 days following the anesthesia procedure
Primary Performance	
Spinal Needle: Assess the incidence of successful needle placement	Percentage of successful needle placement in the subarachnoid space defined as the appearance of cerebrospinal fluid from the spinal needle hub
Secondary	
To assess the incidence of any needle or procedure-related adverse events (other than PDPH)	Incidence of device/procedure-related adverse events including but not limited to: 
 
• Spinal/epidural hematoma
 
• Nerve damage (pain or weakness lower extremities)
 
• Infection (Meningitis, spinal abscess)
 
• Pain, skin redness, irritation at or near the skin puncture site
 
• Backache
 

## 2 Study Description

### 2.1 Study Design

This is a multi-center, prospective, observational, post-market study designed to assess the real-world safety and efficacy of BD Spinal Needles used in an on-market fashion. Up to 150 adult and pediatric participants will be enrolled in the study.

Participants will be screened against study inclusion/exclusion criteria, consented, and enrolled in the study. After enrollment, the participant's demographic and limited medical history will be documented including the reason for the neuraxial procedure. The spinal needle procedure will be performed by the physician investigator.

Participants who withdraw or discontinue the study early (e.g., prior to day-7 post procedure follow-up) may be replaced.

## 2.2 Study Population

Participants will be recruited from the patient population treated at the investigational sites. Sites may choose to limit recruitment to specific areas of the hospital and/or to patients treated by specific healthcare providers. The inclusion/exclusion criteria are described in the protocol Section 5.

## 2.3 Randomization and Blinding

This is a single-arm study and randomization is not applicable.

## 2.4 Sample Size

The primary safety endpoint for spinal needles is the incidence of PDPH with an expected rate ranging from 0.3% to 3% based on literature review. With an incidence of PDPH of 3%, a sample size of 150 participants would lead to a precision of estimate less than 5% using Clopper Pearson exact method (precision of estimate is the distance between point estimate to the upper bound of 95% two-sided exact confidence interval). Additionally, with a sample size of 150 participants, the probability of observing at least one PDPH with is 91.1% when the expected rate of PDPH is 1.6%.

The primary efficacy endpoint for spinal needles is successful placement, defined as the spontaneous appearance of CSF, with an expected rate ranging from 90% to 100% based on literature review. With an expected placement success rate of 90%, a sample size of 150 participants would lead to a precision of estimate at approximately 5% using Clopper Pearson exact method.

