10 STATISTICAL METHODS

The statistical analysis plan will be finalized prior to database lock and will include a more technical and detailed description of the statistical analyses described in the following sections. This section includes a summary of the planned statistical analyses of the primary and secondary endpoints.

Protocol Number: MDS-20EPSPEU001

CONFIDENTIAL

Version: 3.0

Date: 27Apr2022

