# 4 Analysis Population Set(s)

## 4.1 Population Definitions

**Enrolled:** All participants who sign the ICF.

**Evaluable:** All participants in whom a neuraxial procedure is attempted, regardless of success. It will include the following participants in the Spinal Needle Procedure CRF page:

- Was spinal needle procedure performed: Equals ‘Yes’.

**Safety:** All participants on whom an anesthesia procedure is performed. It will include the following participants in the Spinal Needle Procedure CRF page:

- Was there a spontaneous appearance of cerebrospinal fluid (CSF) emerging from the needle hub: Equals ‘Yes’.

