# 5 Statistical Analysis/Calculations

## 5.1 Primary Safety Endpoints

The primary safety endpoint is the incidence of post-dural puncture headache (PDPH) in the 7 days following the anesthesia procedure. It will be computed as the number of participants experiencing the event divided by the total number of patients on whom anesthesia procedure was performed; 95% confidence interval (exact method) will be calculated. The analysis will be performed on the safety population as defined in section 4.1. Subgroup analysis for the primary safety endpoint will also be performed by spinal needle type and gauge if data permits.

The incidence of PDPH will be based on response to the following question in the “Follow-up Assessments” CRF page: “During the required follow-up period, did the subject have a post-dural puncture headache?” Participants experiencing any severity (mild/moderate/severe) of PDPH will contribute to the incidence count in the numerator.

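### The primary safety endpoint (PDPH) has two denominators: all attempted procedures in the protocol, only participants with spontaneous CSF in the SAP

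*SAP*

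**What the plan says.** **Protocol.** Section 10.4 computes the primary safety rate as "the number of participants experiencing the event divided by the total number of evaluable patients", with an exact 95% interval. Section 10.3 defines only two sets, Enrolled and Evaluable, and Evaluable is "All participants in whom a neuraxial procedure is attempted, regardless of success". The opening of section 10 says that the SAP "will include a more technical and detailed description of the statistical analyses described in the following sections".

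**SAP.** Section 5.1 takes the PDPH count "divided by the total number of patients on whom anesthesia procedure was performed" and adds: "The analysis will be performed on the safety population as defined in section 4.1". Section 4.1 builds that Safety population from one CRF item, "Was there a spontaneous appearance of cerebrospinal fluid (CSF) emerging from the needle hub: Equals" Yes. The note to Table 14.2.15 repeats the anesthesia-procedure denominator, and Tables 14.2.15 to 14.2.16d are all headed Safety Population. The SAP also defines Evaluable and uses it for placement success (5.2) and the secondary safety endpoint (5.3), so the two sets are not synonyms.

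**Sample size.** Protocol 10.2 and SAP 2.4 carry the same text. For 150 participants, "the probability of observing at least one PDPH with is 91.1% when the expected rate of PDPH is 1.6" per cent. Placement success is given "with an expected rate ranging from 90% to 100% based on literature review". Protocol 4.1 and SAP 2.1 give 150 as the maximum number enrolled.

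**The concern.** A participant in whom the needle was attempted but no CSF appeared spontaneously is in the protocol's PDPH analysis and outside the SAP's. The exclusion can change the numerator as well as the denominator, because a PDPH reported by such a participant is also dropped. The CRF item that defines the Safety set is the one SAP 5.2 uses to define placement success, so the primary safety set is conditioned on the primary performance outcome.

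Replacing a denominator goes beyond describing the protocol's analysis in more detail. The SAP gives no reason for it, and its revision history records only a change of MedDRA version. PDPH is the primary safety endpoint of a study meant to supply clinical data under EU regulation 2017/745. As the documents stand, two different rates and intervals could each be reported as the planned one.

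**Working it through.** **1. The plan's own figure.** Inputs from SAP 2.4: n = 150, PDPH rate 1.6%.
P(at least one case) = 1 − (1 − 0.016)^150 = 1 − 0.0890 = 0.911. The stated 91.1% reproduces.

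**2. How far the two sets can differ.** Success is expected at 90% to 100%. For illustration, assume 150 attempted procedures; neither document plans that number. The protocol's denominator is then 150, and the SAP's is 150 × 0.90 = 135 up to 150 × 1.00 = 150. At the lower end, 15 attempted participants (10%) leave the PDPH analysis.

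**3. Effect on the endpoint.** Four PDPH cases are assumed among the 150 attempts, with 135 CSF-positive. Intervals are Clopper-Pearson 95%.

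| Definition | Cases / n | Rate | 95% CI |
|---|---|---|---|
| Protocol 10.4, evaluable | 4/150 | 2.7% | 0.7 to 6.7 |
| SAP 5.1, all four cases CSF-positive | 4/135 | 3.0% | 0.8 to 7.4 |
| SAP 5.1, one case without spontaneous CSF | 3/135 | 2.2% | 0.5 to 6.4 |

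The SAP rate is about 0.3 points above the protocol rate in one case (2.96 − 2.67) and about 0.4 points below it in the other (2.67 − 2.22). The direction is not fixed. At 100% success the two definitions coincide.

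**4. Effect on the 91.1%, if the SAP's set is kept.** With 150 attempts and 90% success, n = 135 and 1 − 0.984^135 = 1 − 0.1133 = 0.887. Over the 90% to 100% range the probability is 88.7% to 91.1%, a shortfall of 0 to 2.4 points.

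The 88.7% is not a lower bound. Protocol 7.2 counts a participant as enrolled at consent, and the footnote to Table 14.1.1 reports 15 enrolled participants not treated with the device. If 150 were enrolled and those 15 were not replaced (an assumption), 135 would be evaluable and about 121 to 135 would be in the Safety set. The probability would then be 1 − 0.984^121 = 85.8% up to 88.7%.

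**5. Precision statement.** This is the distance from a 3% rate to the exact upper limit, using beta quantiles with x = 0.03n. It is 4.2 points at n = 150 and 4.5 points at n = 135. With whole cases it is 4.0 (4/150), 4.3 (5/150), 4.4 (4/135) and 4.7 (5/135). All are below the stated 5%.

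**The case against.** The best defence is that the SAP's wording has a root in the protocol. Both endpoint tables describe PDPH after the anesthesia procedure, and protocol section 10 calls itself a summary. Restricting the headache rate to participants with confirmed access to the subarachnoid space may also be a reasonable choice. That stands as an argument for a possible definition. It does not remove the contradiction, because 10.4 names the evaluable set explicitly and 10.3 includes failed attempts in it.

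A second defence is that little depends on the difference. The illustrated shift is a few tenths of a point inside intervals about six points wide, and SAP 2.8 sets no acceptance criteria. This also stands, and it limits the size of the point.

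Three stronger readings are tempting, and the documents support none of them.

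- **The 91.1% is wrong.** It is exact for 150 analysed participants. The sample-size section does not say whether its 150 are enrolled, attempted or analysed.
- **The SAP's set biases the PDPH rate in a known direction.** A smaller denominator raises the rate, and losing cases without spontaneous CSF lowers it. The documents do not say which would dominate.
- **The denominator was changed in response to data.** Some table shells carry realised counts, but nothing dates the choice of the Safety set or links it to results.

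**Conclusion.** The conflict is established from the text alone: protocol 10.3/10.4 against SAP 4.1/5.1 and Table 14.2.15. Up to 10% of attempted participants, and any PDPH among them, are treated differently, on the plan's own success range. The rates in the illustration rest on 150 attempts, 90% success and four cases, and show the size only.

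The sample-size consequence is secondary and conditional. The 88.7% to 91.1% range holds only if the SAP's set is kept and 150 procedures are attempted, whereas the documents cap enrolment at 150. The precision statement of less than 5% holds for 135 to 150 analysed participants. The point should be corrected because it concerns the definition of a primary endpoint. It does not show the study to be too small.

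**What to change.** Use one PDPH denominator in protocol 10.4, SAP 4.1 and 5.1, and the note to Table 14.2.15.

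- **Simplest route.** Run SAP 5.1 and the Table 14.2.15 and 14.2.16 series on the Evaluable set, as the protocol states. Keep the CSF-positive analysis as a labelled supplementary one.
- **If the CSF-positive set stays primary.** Amend protocol 10.3 and 10.4 to define it, give the reason, and report separately any PDPH in attempted participants without spontaneous CSF.
- **Minor, either way.** Say in SAP 2.4 and protocol 10.2 that the 91.1% applies to 150 analysed participants. If the CSF-positive set is kept, add that 150 attempts at 90% to 100% success would give 88.7% to 91.1%, that 150 attempts is an assumption, and that fewer attempts would give less.

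**Cost.** No extra participants and no new data: the CSF item is already on the CRF, and Listing 16.2.9 already lists the PDPH answers for the evaluable population. The simplest route needs a SAP revision and changes to the shells. Any change to protocol text, including the clarification in 10.2, goes through the IRB/EC handling in protocol 14.1.
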